Study Design: Following random assignment to assessment-only or intervention group, subjects will participate in either assessment only or 8-visit group intervention. Groups will vary in size depending on participant recruitment but will not exceed 8. **Intervention:** The group intervention will be an adapted version for our population from the MBCT for the prevention of depression relapse intervention. The main adaptations include 1) substitution of psychoeducation about MDD alone with psychoeducation geared toward trauma and stress physiology and discussion of MDD and PTSD symptoms and 2) no written homework or monitoring, although formal and informal practice during the week and in times of distress will be encouraged. The adapted MBCT will consist of eight, weekly 90-minute group sessions that will involve skills training and in-class practice in: 1) mindfulness techniques including 20-minute meditation exercises; 2) psychoeducation; and 3) feedback and supportive group discussion of exercises. Specific in-class mindfulness exercises will include: a) 'mindful eating', b) brief 'body-scan', c) 'mindful stretching', d) 'mindful walking', e) sitting mindfulness meditation exercises with various objects (breath, sounds, emotional states, thoughts). We are using this adapted version to reduce length of sessions and burden on subjects and enhance feasibility for use in primary care settings. The manualized intervention will be delivered by trained and closely supervised therapists who are overseen by the PI. Group sessions will occur via Zoom. Group guidelines and safety considerations for telehealth group sessions will be reviewed at the start of every group. Participants will be asked to find a private space to participate to protect the confidentiality of other group members. If all group members agree, all group sessions will be

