video recorded to evaluate fidelity and aid in supervision of therapists. At weeks 3, 5, and 7 ED will be assessed given its role as a mechanism of change. **Wait-list Control:** Subjects in the assessment-only group will engage in the pre, post, and follow-up assessments, and an additional brief assessment mid-way between the pre-and post- assessment that will include the same measure of ED that is administered to the intervention group at Week 5. No active treatment will be given to subjects randomized to this condition since the question of clinical interest and practical import at this stage is whether MBCT is more effective than treatment as usual; however subjects will be given the option to participate in the group following participation in the assessments.

Training: All research study therapists will be experienced practicum students in doctoral clinical psychology graduate programs with training in empirically-supported treatment for psychiatric conditions or postdoctoral fellows that have already received a PhD in clinical psychology. These research personnel will be under the supervision of licensed clinical psychologists on the study team who will oversee all treatment and provide weekly supervision on every participant. The study therapists will be trained in all measures being used in the study and will fully understand the goals and purpose of the research proposed.

Risks to Participation: One potential risk is that the participant may be asked to talk about prior experiences and events that may be emotionally difficult to discuss and may bring up distressing feelings. The intervention is not focused on purposefully discussing past traumas; however, mindfulness therapy can increase individuals' awareness of negative thoughts and emotions. Additionally, if at any point during any session, the participant feels uncomfortable, they will always be given the option to stop engagement in group session. Therapists will monitor participants' subjective symptom and distress level at every therapy session and will conduct a risk assessment if symptoms appear to have increased.

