Overall analytic approach: Analyses will be conducted using a combination of R^[99], SAS and MPlus 6.1.^[100] Proposed models capitalize on the benefits (power, minimization of measurement error, minimization of multiple testing) of latent modeling. Interpretation of results will adjust for number of tests performed using the step-down procedure.^[101, 102] MPlus, used to test composite models, permits the use of both frequentist and Bayesian analysis estimation for handling missing data. Bayesian estimation procedures allow multiple imputation of multiple datasets, subsequently used for maximum likelihood estimation with parameter estimates averaged across imputed datasets. Consistent with Kraemer's recommendations for design of intervention development research^[103], the proposed research is focused on evaluating feasibility and acceptability (Aim 1) and preliminary examination of mechanisms of action of the intervention (Aim 2). We expect to meet all Feasibility and Acceptability criteria as demonstrated by acceptable recruitment, retention, and adherence to the intervention and subjects will report that the intervention protocol is acceptable and easy. **Preparing/defining variables:** Data will be examined for assumptions, with estimation procedures applied as a function of data characteristics (Poisson distribution, zero-inflation, etc). Analyses will not impose artificial cutoffs but examine naturally-existing continua, which enhance power and permit the potential identification of nonlinear relationships in which small, cumulative, changes in predictor variables result in large, discontinuous changes in outcomes as predicted by "cusp catastrophe"; we have previously reported such nonlinear influences of early life stress.^[104] Measurement models will be formally tested to assess constructs. If analyses do not support the presence of the expected unitary constructs, subsequent analyses will examine aims as defined by observed variables. Model invariance tests will also be used to assess appropriate statistical treatment of sex;^[105-107] if measurement invariance is not observed, analyses will stratify by sex. Pending model invariance testing, time invariant and time varying covariates will be included in composite models. Analyses will adjust for relevant time varying and time invariant covariates.

Aim 1a: Examine retention and follow-up rates in the intervention and control groups.

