Retention rates will be assessed using session attendance. Previous MBSR interventions among low-income minority populations have yielded completion rates of 53-80%.^[52, 53, 108] Based on 80% completion rates of MBSR in primary care^[46] and 75% completion rates of

MBCT^[45] both in combat vet samples and our anticipated improved accessibility through primary care, I expect that subjects in the intervention group will evidence at least 75% retention and follow-up rates.

Aim 1b: Examine subjects' report of acceptability of and interest in the intervention.

Feasibility and acceptability will be assessed using the Client Satisfaction Questionnaire. We will compare the descriptive statistics and frequency distributions to an established threshold of an average of at least a 3 (mostly satisfied) on subjects' responses. We expect to find that the intervention will meet or exceed expectations.

Aim 1c: Examine barriers to treatment engagement. Barriers to treatment will be assessed using the Perceived Barriers to Psychological Treatment. We will compare our descriptive statistics and frequency distributions to our established threshold of at least one "substantial" barrier (items endorsed as making it extremely difficult or impossible to attend intervention session) on the measure. We expect similar rates of "substantial" barriers in assessment-only and intervention groups, but higher rates of barriers to be related to higher symptom severity of PTSD and MDD.

Aim 2a: Evaluate if MBCT results in greater reductions in ED than wait-list control. In order to examine the impact of intervention on ED, we will conduct LGM with intervention predicting a reduction in ED over the course of the intervention. Specifically, intervention will be regressed on slope and time will be parameterized such that baseline is the intercept and follow-ups are modeled as weeks post baseline.

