Aim 2b: Evaluate if MBCT results in greater normalization of autonomic function than wait-list control. The benefits of LGM will also be applied to our assessment of the effects of intervention on autonomic function, with intervention subjects expected to evidence reduced autonomic arousal to trauma cues at post-intervention and follow-up relative to controls. Specifically, we will conduct an LGM of autonomic arousal to trauma cues, with intervention group regressed on slope such that MBCT subjects are expected to show reduced autonomic arousal to cues (negative slope) relative to control subjects who are expected to show little to no change over time in arousal.

C.4) Power Analysis. Statistical power was calculated using G-Power 3.1.2. As described above, proposed analyses are tailored to each aim and are designed, in part, to maximize power and minimize multiple-testing errors through the use of LGM. However, it is difficult to provide *a priori* estimates of power for full models given that power depends on multiple parameters that are difficult to specify prior to the analyses. Accordingly, both for space constraints and conservative minimization of assumptions regarding power gains, we estimate power using a multiple regression framework. Please note that building on published latent factor and latent growth

simulations,^[109] we did conduct a few Monte Carlo simulations and were able to confirm that our power is enhanced (with most simulations showing power of .99, assuming expected medium sized effects) using the proposed analyses. We also summarize across aims, to conserve space as well as minimize assumptions. Defined by Cohen,^[110] conventions for describing effect sizes for multiple regression (R^2) are .02 for a small effect, .15 for a moderate effect, and .35 for a large

[figure not shown]

Figure 1. Effect size justification for proposed sample.

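### MBCT is delivered in therapy groups of up to 8, but the Aim 2 growth models and the power calculation treat all participants as independent

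*Combined protocol and SAP*

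**What the plan says.** The Study Design section delivers MBCT only in groups, over eight weekly sessions that include group discussion. On size it says: "Groups will vary in size depending on participant recruitment but will not exceed 8". The Wait-list Control paragraph gives the other arm no active treatment: "Subjects in the assessment-only group will engage in the pre, post, and follow-up assessments", plus one brief mid-way measure of emotion dysregulation (ED). They may join a group only after those assessments.

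For Aim 2a the Statistical analysis section states that "we will conduct LGM with intervention predicting a reduction in ED over the course of the intervention", with arm related to slope. Aim 2b uses the same structure for skin conductance response to trauma cues. Neither paragraph mentions therapy group, therapist, a cluster-robust standard error or an ICC. The overall analytic approach adds that "Analyses will adjust for relevant time varying and time invariant covariates" and a step-down procedure for the number of tests.

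On sample size, the Power Analysis says "we estimate power using a multiple regression framework". It includes no design effect. Some Monte Carlo runs are mentioned, but their structure is not described.

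**The concern.** This is a partially nested design. MBCT participants share peers, sessions and therapists, while wait-list participants share nothing comparable during the comparison. A growth model with arm as predictor of slope handles correlation within a person over time. It does not handle correlation between people in the same therapy group. If that correlation is positive, the plan as written understates the variance of the MBCT arm's mean slope.

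The other provisions do not fill the gap:

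- The covariate clause names no group term. Therapy group as a fixed covariate would not serve, because groups exist only within MBCT and are confounded with arm.
- The step-down procedure corrects for the number of tests. It cannot repair p-values that are individually too small.

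This matters because the plan intends inference from Aim 2. The Wait-list Control paragraph says that "the question of clinical interest and practical import at this stage is whether MBCT is more effective than treatment as usual", and the Power Analysis expects to detect significant effects. With a positive ICC, p-values and confidence intervals for ED and skin conductance would overstate the evidence.

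**Working it through.** **Inputs from the documents.** Target N is 80 (Population). Group size is at most 8 (Study Design). The cited effect range is d = 0.59 to 0.99, which is for PTSD and depression symptoms rather than ED (Power Analysis). Aim 1a states: "I expect that subjects in the intervention group will evidence at least 75% retention and follow-up rates".

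**Assumptions not in the documents.** Allocation 1:1 (40 v 40, hence at least 40/8 = 5 groups), two-sided 5% level, average group size m of 3 to 8, and ICC of 0 to .10 on subject-level slopes.

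**The plan's own power figure.** The plan gives power .80 at f² = .25 with N = 80. An omnibus regression F test (noncentrality f²N, 5% level) gives .993 with 1 predictor, .935 with 5, .838 with 10, .817 with 11 and .797 with 12. The stated .80 therefore matches about 11 to 12 predictors, a number the plan does not give. It can be neither confirmed nor called wrong, and this point does not depend on it.

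**Size of the unclustered test.** With complete balanced data, the arm-on-slope test corresponds to a two-sample t-test on subject slopes. The design effect applies in the MBCT arm only:

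- DE = 1 + (m − 1) × ICC
- true/reported SE = √((DE + 1)/2)
- actual type I error = 2 × [1 − Φ(1.96 / SE ratio)]

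For m = 8 and ICC .05: DE = 1 + 7 × .05 = 1.35; SE ratio = √1.175 = 1.084; 1.96/1.084 = 1.808; type I error .071. For ICC .10: DE = 1.70; SE ratio = √1.35 = 1.162; 1.96/1.162 = 1.687; type I error .092.

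| m | DE (ICC .05 / .10) | SE ratio | Type I error |
|---|---|---|---|
| 3 | 1.10 / 1.20 | 1.025 / 1.049 | .056 / .062 |
| 4 | 1.15 / 1.30 | 1.037 / 1.072 | .059 / .068 |
| 5 | 1.20 / 1.40 | 1.049 / 1.095 | .062 / .074 |
| 8 | 1.35 / 1.70 | 1.084 / 1.162 | .071 / .092 |

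**Simulation check** (100,000 trials per scenario, pooled t-test ignoring group):

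| Arms | Groups | Type I error (ICC .05 / .10) |
|---|---|---|
| 40 v 40 | five of 8 | .071 / .092 |
| 40 v 40 | eight of 5 | .062 / .074 |
| 40 v 40 | ten of 4 | .059 / .069 |
| 40 v 40 | 8, 8, 8, 6, 4, 3, 3 | .065 / .084 |
| 30 v 30 | five of 6 | .064 / .079 |
| 30 v 30 | eight of 3–4 | .059 / .065 |
| 30 v 30 | ten of 3 | .056 / .062 |

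At ICC .01 the error is .051 to .054, and at ICC 0 there is no excess. The 30 v 30 rows apply 75% to both arms (40 × .75 = 30) as an illustration.

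**A test that respects groups.** Comparing MBCT group means with individual controls, with Satterthwaite degrees of freedom, gave type I error of .049 to .055 across the scenarios, including the unequal group sizes.

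**The case against.** The strongest reply is about size and weight.

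- **Upper end.** About 9% needs full groups of 8 and an ICC of .10. Eight is a ceiling, and wait-list participants who later join might take places, leaving fewer analysed members per group. With groups of 4 to 5 the range is about .059 to .074. This stands.
- **No ICC in the documents.** A negligible effect cannot be excluded. This also stands; the claim is conditional.
- **Error-free slopes.** If the ICC applies to true slopes and half the observed slope variance is measurement error, the effective ICC halves to .025 / .05. For m = 8, DE = 1 + 7 × .025 = 1.175 gives .060, and ICC .05 gives .071. For m = 4 the figures are .054 and .059. The excess shrinks but does not vanish.
- **30 v 30.** The 75% refers to the intervention arm, and the plan describes imputation and maximum likelihood rather than a completers' analysis. Fair; those rows are only illustrative.
- **Preliminary aim.** The plan puts feasibility first and calls the Aim 2 work preliminary. That limits the consequence. It does not justify standard errors that leave out a known feature of the design.
- **Few groups.** With five groups of 8 and a true ICC of .05, 95% of ICC estimates fall between −.12 and .31. The ICC will be poorly estimated. That is a reason to settle the model in advance.

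None of these supplies the missing term.

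**Conclusion.** The concern holds. The stated Aim 2 analyses ignore clustering that exists in one arm only, so their standard errors are too small under any positive ICC. Under the assumptions listed, the understatement of the standard error ranges from about 2.5% (groups of 3, ICC .05) to 16% (groups of 8, ICC .10). A nominal 5% test then runs at about 5.6% to 9.2%, with mid-range group sizes giving roughly 6% to 7%. The treatment-effect estimates are mainly unaffected, and Aim 1 largely so. It should be fixed before analysis; it does not undermine the trial.

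**What to change.** Record the therapy-group ID for every MBCT participant. Specify Aims 2a and 2b as partially nested models: a random group effect on slope in the MBCT arm only, each wait-list participant a singleton, and Satterthwaite or Kenward-Roger degrees of freedom. This can be an equivalent mixed model in SAS, which the plan already lists, alongside the MPlus growth model. Report the ICC with its interval and say that 5 to 10 groups make it imprecise. Restate power over ICCs of, for example, 0 to .10.

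Also state what happens if the group variance is estimated as zero, which occurred in 28–44% of simulated trials at ICC .05–.10. Bounding it at zero and pooling in that case gave type I error of .041 to .048; this was checked for equal-sized groups only.

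The cost is one variable, SAP wording and a second model formulation, with no extra patients or visits. The real price is power. These figures are for d = 0.59 and the group-means test; the full mixed model was not simulated.

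| Arms | Independence | ICC .05 | ICC .10 |
|---|---|---|---|
| 40 v 40 | .74 | .60–.69 | .54–.66 |
| 30 v 30 | .61 | .51–.57 | .46–.55 |

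Even at ICC 0, power with 40 v 40 is .69–.72, or .67 with the unequal groups above. Part of the loss under a positive ICC is uncertainty that the current plan leaves out: at m = 8 a normal approximation that treats the ICC as known already drops power from .75 to .68 (ICC .05) or .62 (ICC .10).

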staff members who will conduct the CAPS and MINI (to assess other Axis I disorders) will be blind to group assignment. The time requirement for the MBCT intervention group will be eight 90-minute sessions. Groups will be offered virtually. Subjects will be compensated \$10 for their time at each intervention session. Upon the completion of the 8 sessions (MBCT group) or 8 weeks after the pre-intervention assessment (assessment-only wait-list group), a post-intervention assessment will be conducted. Again, this may occur in person or virtually depending on COVID-19 conditions. One month later, a follow-up assessment will be conducted by phone or Zoom. The time requirement for the pre and post assessment will be ~3 hours and subjects will be compensated \$60 for these assessments. The follow up assessment will take approximately one hour and subjects will be compensated \$20 for that assessment.

Measures	Screen	Pre	Intervention (8 weeks)								Post	FU
			1	2	3	4	5*	6	7	8		
Traumatic Events Inventory	X											
Alcohol Use Disorders Identification Test	X											
Drug Abuse Screening Test	X											
Primary Care PTSD Screen	X										X	X
Patient Health Questionnaire-9	X										X	X
PTSD Checklist for DSM-5	X										X	X
Beck Depression Inventory, II	X										X	X
Standardized Trauma Interview (+ SC)		X									X	X
Difficulties in Emotion Regulation Scale		X		X	X		X		X		X	X
Clinician Administered PTSD Scale	X										X	
MINI International Neuropsychiatric Interview	X										X	
Five Facet Mindfulness Questionnaire	X										X	X
Self Compassion Scale, Short Form	X										X	X
PANAS	X										X	X
Client Satisfaction Questionnaire											X	
Perceived Barriers to Psychological Treatments											X	
Post-group Follow-up Questionnaire**											X	

*Assessment-only subjects will also fill out measures for intervention week 5.

**For group intervention participants only

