In addition to monitoring participants within the sessions, therapists will provide information at the first session of treatment for what the participant should do if they experience a significant increase in symptoms or have any emotional problems outside of their study visit. This information will include the therapist's work phone number where they can be reached during business hours (8:00am - 5:00pm), as well as the phone number for the Georgia Crisis and Access Line, which is a 24-hour hotline with licensed psychologists and social workers who can take crisis calls and provide immediate assistance should the participant need it. Throughout the study, participants will be reminded of these resources.

Benefits to Subject: One potential benefit is that the participants will see a decrease in depression and/or PTSD symptoms and will be better able to function day-to-day. Additionally, this study may provide insight into how treatment can affect emotion regulation, depression, and PTSD and may inform treatment options particularly in low-income populations in the future.

Participant selection

Population: Participants will be men and women between the ages of 18 and 65, recruited from Grady Memorial Hospital medical clinics. Grady Memorial Hospital is an inner-city hospital in downtown Atlanta, GA (Target N=80).

Subject Inclusion/Exclusion Criteria and Rationale: **Inclusion criteria.** 1) Ability to provide informed consent, 2) Willingness to participate in study, 3) Self-identity as African American, 4) 18-65 years old, 5) History of childhood and/or adult trauma exposure (3 total criterion A traumas) 6) positive PTSD screen (PC-PTSD ≥ 3), and 7) positive MDD screen (PHQ-9 ≥ 5). **Exclusion criteria.** 1) Presence of intellectual disability, bipolar, or psychotic disorder; and 2)

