The PI and study personnel have completed and passed the Human Subjects Protection Education Program provided by Emory University. Certification letters will be provided upon request. The present study is an intervention study and therefore we will complete a data safety monitoring plan to ensure oversight and monitoring of the study to ensure the safety of participants and the validity and integrity of the data. The PI will monitor safety issues throughout the study. Specifically, study progress and safety will be reviewed weekly (and more frequently if needed). The PI will work closely with [name] to monitor for potential adverse reactions of subjects to mindfulness exercises and if significant exacerbation of symptoms or safety concerns emerge, the subject will be offered immediate psychological services through the Grady Health System and NIA project. Progress reports, including subject recruitment, retention/attrition, and adverse events (AE) will be provided to an Independent Monitor (IM) semi-annually. The IM for this study will be the Data Safety Monitoring Board in the Department of Psychiatry and Behavioral Sciences. An Annual Report will be compiled and will include a list and summary of AEs. In addition, the Annual Report will address (1) whether AE rates are consistent with pre-study assumptions; (2) reason for dropouts from the study; (3) whether all participants met entry criteria; (4) whether continuation of the study is justified on the basis that additional data are needed to accomplish the stated aims of the study; and (5) conditions whereby the study might be terminated prematurely. The Annual Report will be sent to the IM and will be forwarded to the IRB.

Confidentiality

Confidentiality will be protected throughout the study and following completion of the study. This will be done in a number of ways. First, all participants will be assigned a subject ID and all data gathered and session notes will only contain de-identified information and their subject ID. Also, participants will be informed of the confidential nature of the study and informed of the limitations of confidentiality. Also, all participant information will be kept in a locked desk drawer in a locked office or stored on a password protected and secured electronic network.

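### Adverse events are looked for more closely in MBCT attenders than in anyone else, and the rate they are to be judged against is not stated

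*Combined protocol and SAP*

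**What the plan says.** **Benchmark.** The Data and Safety Monitoring Plan requires an Annual Report that lists and summarizes AEs and addresses, as its first item, "whether AE rates are consistent with pre-study assumptions". No section gives such a rate, a threshold or a source for one. No AE definition, elicitation question, grading or attribution rule, or by-arm presentation is described.

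**MBCT arm.** Under Risks to Participation: "Therapists will monitor participants' subjective symptom and distress level at every therapy session". A risk assessment follows if symptoms seem to have risen. For problems between visits, "therapists will provide information at the first session of treatment for what the participant should do"; this covers the therapist's office-hours number and a 24-hour crisis line, with later reminders. The monitoring plan also has the PI "monitor for potential adverse reactions of subjects to mindfulness exercises".

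**Wait-list arm.** The Wait-list Control paragraph describes one brief contact between the Pre and Post assessments, said to include the emotion dysregulation measure. The footnote to the schedule of measures agrees: "Assessment-only subjects will also fill out measures for intervention week 5". No AE inquiry is described there.

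**Both arms.** The PI reviews safety weekly. PHQ-9, PC-PTSD, PCL-5 and BDI-II are scheduled at Screen, Post and follow-up, and the group-only footnote is not attached to any of them. CAPS and MINI are repeated at Post by interviewers blind to group. Nothing says that these scores feed the safety reports.

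**The concern.** All subjects enter with positive PTSD and depression screens, so some will worsen whatever they are assigned to. A count of worsening among MBCT subjects therefore says little about the mindfulness exercises unless it can be set against an expected rate or against a control count collected in the same way. The plan names the first without giving a value. For the second, it describes regular checks in one arm and none in the other.

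The distortion could run in either direction. MBCT could appear to produce more AEs because attenders are seen weekly. It could also appear safer than it is if people worsen, stop attending and so lose the session check. The Independent Monitor would have no ready way to separate either artefact from a real effect.

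**Working it through.** The documents give no AE rate, safety threshold or safety power, so there is no planned figure to reproduce. The calculation below is an illustration, and every detection probability in it is an assumption.

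**Inputs from the documents**
- Total sample 80. The allocation ratio is not stated; 40 per arm is assumed.
- Expected retention in the intervention arm: at least 75% (Aim 1a, where retention is assessed by session attendance).
- Completion rates cited from earlier programmes: 53-80% (Aim 1a).

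**Assumed inputs**
- The true AE rate is the same in both arms (no harm).
- Detection is 0.90 in MBCT attenders, and d in MBCT non-attenders and wait-list subjects, with d = 0.25 or 0.50.

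**Formula.** With attendance a:

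- MBCT detection = 0.90a + d(1 − a)
- Wait-list detection = d
- Apparent rate ratio = [0.90a + d(1 − a)] / d

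The true rate cancels from the ratio.

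| Attendance | d = 0.25 | d = 0.50 |
|---|---|---|
| 53% | 0.5945 / 0.25 = 2.38 | 0.712 / 0.50 = 1.42 |
| 75% | 0.7375 / 0.25 = 2.95 | 0.800 / 0.50 = 1.60 |
| 80% | 0.770 / 0.25 = 3.08 | 0.820 / 0.50 = 1.64 |

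**In counts.** At an assumed true rate of 10%, each arm of 40 has 4 events. At 75% attendance and d = 0.25, MBCT would record 4 × 0.7375 = 2.95 and wait-list 4 × 0.25 = 1.0. At d = 0.50 the figures are 3.2 and 2.0.

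**Leaving session observation.** At 75% retention, 40 × 0.25 = 10 MBCT subjects no longer have the session check.

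**What the sample can show even with equal collection (40 per arm assumed)**
- No AEs in 40 subjects: one-sided 95% upper bound 1 − 0.05^(1/40) = 7.2%. With 30 subjects it is 9.5%.
- Power at two-sided 0.05 for 20% versus 10%: 24% (normal approximation) or 16% (Fisher).
- Power for 30% versus 10%: 61% or 53%.

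Equal collection would therefore remove the detection artefact, but the comparison would remain descriptive.

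**The case against.** The plan schedules no between-arm AE test. It asks for a listing and summary, in a trial aimed at feasibility, acceptability and preliminary mechanisms. A formal comparative safety analysis would be beyond its purpose and badly underpowered. That is correct, and the remedy below is limited to descriptive tables. But a rate that is to be compared with expectation still has to be collected in a known way, and a randomized control arm invites comparison whether or not a test is planned.

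Four stronger readings are tempting, and the documents do not support them.

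- *Detection depends wholly on attending sessions.* The PI reviews safety weekly, and MBCT subjects have telephone routes outside sessions. The Annual Report must also cover why subjects dropped out, and attrition goes to the monitor semi-annually. What is missing is any account of how events in wait-list subjects or non-attenders would reach that review.
- *The trial cannot tell whether MBCT does harm.* Self-report scales in both arms at Post and follow-up, and blinded interviews at Post, could show worsening. The PHQ-9 suicide item already triggers a clinician assessment, at least at screening. The gap is that the scale scores are not routed into safety reporting.
- *Eight sessions against one mid-point contact means an eightfold artefact.* That needs every MBCT subject at every session, perfect detection there, week-long events and no later recall. It also ignores the Post assessment, which wait-list subjects have eight weeks after Pre. Counting Post, coverage is 2 of 8 weeks and the ratio 4. With 75% attending, and non-attenders seen like wait-list subjects, it is (0.75 + 0.25 × 0.25) / 0.25 = 3.25.
- *The decision to continue rests on the AE comparison.* The Annual Report ties continuation to whether more data are needed for the aims; AE rates are a separate item.

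The benchmark may also exist elsewhere. The text says that a data safety monitoring plan will be completed and cites a Protection of Human Subjects section that was not among the documents reviewed. The supportable statement is that the rate is not stated in the documents supplied.

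**Conclusion.** The concern holds in a limited form. AE ascertainment as described differs by arm and by attendance, and the named benchmark has no stated value. The AE summary therefore cannot support a fair between-arm reading or a check against expectation, although other sources give partial information.

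With no true harm, unequal detection alone would give an apparent rate ratio of about 1.6 to 3.0 at 75% attendance, and about 1.4 to 3.1 over 53-80%. These figures rest on assumed detection of 90% in attenders and 25% to 50% in everyone else; the ratio moves towards 1 as the two approach each other. The direction is secure if attenders are in fact watched more closely, but the size is illustrative. The change is worth making because it is inexpensive and bears on safety. The gap does not invalidate the trial.

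**What to change.** 1. Ask one identical question about AEs and worsening in both arms at the contacts they share (mid-point, Post and follow-up), regardless of session attendance. Placing it in the self-report battery would help keep the CAPS and MINI interviewers blind.
2. Report the AEs from those shared contacts by arm. List session-detected events separately as MBCT-only, and do not use them for the between-arm reading.
3. Add to the Annual Report the number in each arm whose PHQ-9 and PCL-5 worsened from Screen to Post and from Screen to follow-up, with the definition of worsening fixed in advance. These scales are already scheduled.
4. In the Data and Safety Monitoring Plan, either state or cite the expected AE rate and its source, or name the concurrent wait-list arm as the reference.

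**Cost.** One short question that slightly lengthens the mid-point contact, by-arm tables going to the monitor, and a few sentences of protocol text. No treatment or clinical rule changes. With about 40 per arm (assumed), the tables would reveal only large excesses and should be labelled descriptive.
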